Objectives	Endpoints

 To evaluate the effect of treatment with mirikizumab on achieving corticosteroid-free remission without surgery among patients in clinical remission at Week 52 and receiving corticosteroids at baseline 	
 The proportion of patients who are in MMS clinical remission at Week 52 without the use of corticosteroids 
CCI

 To evaluate the effect of treatment with mirikizumab on PUCAI clinical remission at Week 12 and/or Week 52 	
 The proportion of patients in PUCAI clinical remission at Week 12 The proportion of patients in PUCAI clinical remission at Week 52 The proportion of patients in PUCAI clinical remission at Week 12 who achieve clinical remission at Week 52 The proportion of patients in PUCAI clinical response at Week 12 who achieve clinical remission at Week 52 
PUCAI clinical remission is defined as a PUCAI score of <10 points
 
PUCAI clinical response is defined below

 To evaluate the effect of treatment with mirikizumab on PUCAI clinical response at Week 12 and/or Week 52 	
 The proportion of patients in PUCAI clinical response at Week 12 The proportion of patients in PUCAI clinical response at Week 52 The proportion of patients in PUCAI clinical response at Week 12 who achieve PUCAI clinical response at Week 52 
PUCAI clinical response is defined as a reduction in baseline PUCAI score of ≥ 20 points

 To evaluate the effect of treatment with mirikizumab on achieving endoscopic remission at Week 12 and/or Week 52 	
 The proportion of patients in endoscopic remission at Week 12 The proportion of patients in endoscopic remission at Week 52 The proportion of patients in endoscopic remission at Week 12 who maintain endoscopic remission at Week 52 (durable endoscopic remission) 
Endoscopic remission is defined as:
 
 ES = 0 or 1 (excluding friability)

 To evaluate the effect of treatment with mirikizumab on achieving ES = 0 at Week 12 or Week 52 	
 The proportion of patients with ES = 0 at Week 12 The proportion of patients with ES = 0 at Week 52

Objectives	Endpoints

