4.2. Secondary Objectives

Table AMBU.4.2 shows the protocol-defined secondary objectives and endpoints of the study. In addition, the analysis of other exploratory endpoints are described in Section 4.3 and Section 6.10.

The estimand (ICH 2019) associated with each endpoint/analysis is documented in the following places:

- The population of interest is described in the protocol inclusion/exclusion criteria and in this document in Section 6.1.1 and Table AMBU.6.4.
- The endpoint/variables may be found in Table AMBU.4.2 and Table AMBU.6.4.
- The handling of intercurrent events and missing data may be found in Section 6.3 and Table AMBU.6.4.
- Population summary measures are described in Section 6.1.3, Table AMBU.6.5, and Table AMBU.6.6.

 Table AMBU.4.2.
 Secondary Objectives and Endpoints

Objectives	Endpoints
Secondary	
To evaluate the effect of treatment	The proportion of patients in modified Mayo score (MMS) clinical
with mirikizumab on achieving	remission at Week 12
clinical remission at Week 12	The proportion of patients in MMS clinical remission at Week 52
and/or Week 52	The proportion of patients in MMS clinical remission at Week 52
	among the MMS clinical remitters at Week 12 (durable clinical
	remission)
	The proportion of patients in MMS clinical remission at Week 52
	among the MMS clinical responders from Week 12
	MMS clinical remission is defined as:
	Stool frequency (SF) subscore = 0 , or SF = 1 , and
	Rectal bleeding (RB) subscore = 0, and
	Endoscopic subscore (ES) = 0 or 1 (excluding friability)
	MMS clinical response is defined below

Objectives	Endpoints
Secondary	
To evaluate the effect of treatment with mirikizumab on achieving clinical response at Week 12 and/or Week 52	The proportion of patients in clinical response at Week 12 The proportion of patients in clinical response at Week 52 The proportion of patients in clinical response at Week 12 who achieve clinical response at Week 52 Clinical response is based on the MMS and is defined as: A decrease in the MMS of ≥2 points and ≥30% decrease from baseline, and A decrease of ≥1 point in the RB subscore from baseline or a RB score of 0 or 1

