To evaluate the effect of treatment with mirikizumab on achieving corticosteroid-free remission without surgery among patients in clinical remission at Week 52 and receiving	The proportion of patients who entered the study on corticosteroids and who are in MMS clinical remission at Week 52 without the use of corticosteroids Corticosteroid-free remission without surgery at Week 52 defined as:
corticosteroids at baseline	
To evaluate the effect of treatment with mirikizumab on PUCAI clinical remission at Week 12 and/or Week 52	The proportion of patients in PUCAI clinical remission at Week 12 The proportion of patients in PUCAI clinical remission at Week 52 The proportion of patients in PUCAI clinical remission at Week 12 who achieve clinical remission at Week 52 The proportion of patients in PUCAI clinical response at Week 12 who achieve clinical remission at Week 52 PUCAI clinical remission is defined as a PUCAI score of <10 points PUCAI clinical response is defined below
To evaluate the effect of treatment with mirikizumab on PUCAI clinical response at Week 12 and/or Week 52	The proportion of patients in PUCAI clinical response at Week 12 The proportion of patients in PUCAI clinical response at Week 52 The proportion of patients in PUCAI clinical response at Week 12 who achieve PUCAI clinical response at Week 52 PUCAI clinical response is defined as a reduction in baseline PUCAI score of ≥20 points
To evaluate the effect of treatment with mirikizumab on achieving endoscopic remission at Week 12 and/or Week 52	The proportion of patients in endoscopic remission at Week 12 The proportion of patients in endoscopic remission at Week 52 The proportion of patients in endoscopic remission at Week 12 who maintain endoscopic remission at Week 52 (durable endoscopic remission) Endoscopic remission is defined as: ES = 0 or 1 (excluding friability)
To evaluate the effect of treatment with mirikizumab on achieving ES = 0 at Week 12 or Week 52	The proportion of patients with ES = 0 at Week 12 The proportion of patients with ES = 0 at Week 52
To evaluate the effect of treatment with mirikizumab on symptomatic remission over time	Proportion of patients in symptomatic remission at applicable study visits $ \begin{aligned} & \textbf{Symptomatic remission} \text{ is defined as:} \\ & \textbf{SF} = 0, \text{ or SF} = 1 \text{ with a} \geq 1 \text{-point decrease from baseline and} \\ & \textbf{RB} = 0 \end{aligned} $

Objectives	Endpoints
Secondary	

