6.1.1. Analysis Populations

Patient populations are defined in Table AMBU.6.1 along with the analysis they will be used to conduct. Patients will be analyzed according to the weight/treatment dose group to which they were assigned for all populations, found in Table AMBU.6.2.

Table AMBU.6.1. Definition of Population

Population	Description
Efficacy and Health Outcomes	
Modified Intent-to-Treat (mITT) Population	All enrolled patients that received at least 1 dose of treatment, even if the patient does not receive the correct dose, or otherwise does not follow the protocol. Patients will be analyzed according to the treatment to which they were assigned. Unless otherwise noted, efficacy and health outcomes analyses will be conducted on this population.
Safetya	All patients who received at least 1 dose of the study drug. Patients will be
Salety	analyzed according to the weight/treatment dose group to which they were assigned.
Pharmacokinetics	
PK evaluable	All patients who received at least 1 dose of investigational product and have
	sufficient blood sampling to allow for PK evaluation.

Abbreviation: PK = pharmacokinetic.

Table AMBU.6.2. Weight/Treatment Dose Groups for Each Analysis Study Period and Population

Study Period	Analysis Population	Weight/Treatment Dose Groups
Induction Period	mITT; Safety	≤40 kg 5mg/kg miri IV; ≤40 kg 10mg/kg miri IV; >40 kg 300mg miri IV; All miri
Induction and Maintenance Periods	mITT; Safety	≤40 kg 5mg/kg miri IV; ≤40 kg 10mg/kg miri IV; >40 kg 300mg miri IV; All miri
Maintenance Period	mITT	≤20 kg 50mg miri SC >20 kg and ≤ 40 kg 100mg miri SC >40 kg 200 mg miri SC; ≤20 kg NR 10mg/kg miri IV & 50mg miri SC >20 kg and ≤ 40 kg NR 10mg/kg miri IV & 100mg miri SC >40 kg NR 300mg miri IV & 200 mg miri SC; All miri

Abbreviations: IV = intravenous; mITT = modified intent-to-treat; miri = mirikizumab; NR = non-responder (at Week 12); SC = subcutaneous.

The weight/treatment dose groups shown in Table AMBU.6.2 reference the specific treatment regimens to which pediatric patients are assigned at Week 0 (for the induction period) and at Week 12 (for the maintenance period) and are dependent on the participants' weight at those respective visits and their clinical response status at Week 12 for the maintenance period as

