		Endoscopic Response	A decrease in the ES of ≥1 point compared to baseline.	Missing if ES is missing.
		SF component of clinical remission	SF = 0, or $SF = 1$	Missing if SF is missing.
		RB component of clinical remission	RB = 0	Missing if RB is missing.
		Corticosteroid-free remission at Week 52	Corticosteroid-free remission without surgery at Week 52, defined as: Clinical remission at Week 52, and No corticosteroid use or UC-related surgery for ≥12 weeks prior to Week 52	NRI if any component is missing.
		Loss of Clinical Response	CCI	

Measure	Description	Variable	Derivation / Comment	Definition of Missing
Urgency NRS	CCI	Urgency NRS Score	Calculated by averaging data from all available diary entries of Urgency NRS for a 7 day period as described in Appendix 1.	Missing if fewer than 4 available measurements in the relevant 7 days (see Appendix 1).
Abdominal Pain NRS	The Abdominal Pain NRS is a single patient-reported item that measures the "worst abdominal pain in the past 24 hours" using a 6-point scale ranging from 0 (no pain) to 5 (worst possible pain) for 8-11 years old, and 11-point NRS ranging from 0 (no pain) to 10 (worst possible pain) for children < 8 years old as completed by a caregiver and those 12-17 years old.	Abdominal Pain NRS Score	Calculated by averaging data from all available diary entries of Abdominal Pain NRS for a 7 day period as described in Appendix 1.	Missing if fewer than 4 available measurements in the relevant 7 days.
PGIC	The Patient's Global Impression of Change (PGIC) scale is a patient-rated instrument designed to assess a patients' rating of change in their symptom(s). Responses are graded on a 7-point Likert scale. Patients or caregivers will record their response on the PGIC electronically as source data in the tablet device at appropriate visits.	PGIC Score	Single Item	Single item, missing if missing. No imputation.
PGRS	Patient's Global Rating of Severity (PGRS) is a 1-item patient-rated questionnaire designed to assess the patients' rating of their disease symptom severity over the past	PGRS Score	Calculated by averaging data from all available diary entries of PGRS for a 7 day period as described in Appendix 1.	Missing if fewer than 4 available measurements in the relevant 7 days.

Measure	Description	Variable	Derivation / Comment	Definition of Missing

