	medical history and adverse event eCRFs. Extraintestinal manifestations include, but are not limited to: uveitis, peripheral arthritis, ankylosing spondylitis, aphthous stomatitis, arthralgia, autoimmune hepatitis, cholelithiasis, deep vein thrombosis, iritis, nephrolithiasis, erythema nodosum, osteopenia, osteoporosis, pancreatitis, sclerosing cholangitis, pyoderma gangrenosum, sacrolitis and skin vasculitis NOS.	Resolution of Baseline EIMs	Complete resolution of baseline EIMs at Week 12 or 52. If a patient has multiple baseline EIMs, then at least one of the EIMs must have resolved.	No Imputation

Abbreviations: CFB = change from baseline; NOS = not otherwise specified; NRI = non-responder imputation; NRS = Numeric Rating Scale; PUCAI = Pediatric Ulcerative Colitis Activity Index; Q12W = every 12 weeks.

 Table AMBU.6.5.
 Description of Secondary Efficacy/Health Outcomes Analyses

		Analysis Method	Population	
Measure	Variable	(Section 6.1.3)	(Section 6.1.1)	Time Point(s)
Mayo Score and components	MMS Clinical Remission	Proportion for each weight/treatment dose group along with the 95% 2-sided CI with NRI and as observed	mITT	Weeks 12 and 52
			mITT who are remitters from	Week 52
			Week 12	
			mITT who are MMS clinical	Week 52
			responders from Week 12	
	MMS Clinical Response	Proportion for each weight/treatment	mITT	Weeks 12 and 52
		dose group along with the 95%	mITT who achieve MMS	Week 52
		2-sided CI with NRI and as observed.	clinical response at Week 12	
	Corticosteroid-free	Proportion for each weight/treatment	mITT	Week 52
	remission	dose group along with the 95%		
		2-sided CI with NRI and as observed.		
	Endoscopic Remission	Proportion for each weight/treatment	mITT;	Weeks 12 and 52
		dose group along with the 95%	mITT who are in endoscopic	Week 52
		2-sided CI with NRI and as observed.	remission at Week 12	
	Endoscopic subscore of 0	Proportion for each weight/treatment	mITT	Weeks 12 and 52
		dose group along with the 95%		
		2-sided CI with NRI and as observed.		
	Symptomatic remission	Proportion for each weight/treatment	mITT	At all scheduled visits
		dose group along with the 95%		
		2-sided CI with NRI and as observed.		
PUCAI	PUCAI clinical remission	Proportion for each weight/treatment	mITT	Weeks 12 and 52
		dose group along with the 95%	mITT who achieve PUCAI	Week 52
		2-sided CI with NRI and as observed.	clinical remission at Week 12	
			mITT who achieve PUCAI	Week 52
			clinical response at Week 12	

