Abbreviations: CFB change from baseline; CI = confidence interval; mBOCF = modified baseline observation carried forward; mITT = modified intent-to-treat; MMS = Modified Mayo Score; NRI = non-responder imputation; NRS = Numerical Rating Scale; PUCAI = Pediatric Ulcerative Colitis Activity Index; Q12W = every 12 weeks.

 Table AMBU.6.6.
 Description of Exploratory Efficacy/Health Outcomes Analyses

Measure	Variable	Analysis Method (Section 6.1.3)	Population (Section 6.1.1)	Time Point(s)
Mayo Score and components	Change from baseline in SF, RB, and Total Symptomatic Score	Descriptive statistics and 95% CI for mean with mBOCF and as observed.	mITT	At each scheduled visit
	Change from baseline in ES	Descriptive statistics and 95% CI for mean with mBOCF and as observed.	mITT	Weeks 12 and 52
	Time to first symptomatic response	Descriptive statistics and 95% CI for mean.	mITT	During Induction Period
	Time to first symptomatic remission	Descriptive statistics and 95% CI for mean.	mITT	During Induction Period
	MMS Alternative Clinical Remission	Proportion for each weight/treatment dose group along with the 95% 2-sided CI with NRI and as observed.	mITT	Weeks 12 and 52
CRP	CRP CFB	Descriptive statistics and 95% CI for mean with mBOCF and as observed.	mITT	Week 12 Week 52
Fecal calprotectin	Fecal calprotectin CFB	Descriptive statistics and 95% CI for mean with mBOCF and as observed.	mITT	Week 12 Week 52
PGIC	Mean PGIC Score	Descriptive statistics and 95% CI for mean as observed.	mITT	Week 4, Week 8, Week 12, and Week 52
PGRS	PGRS Score CFB	Descriptive statistics and 95% CI for mean with mBOCF and as observed.	mITT	At each scheduled visit.
Nocturnal Stool	Nocturnal Stool Score CFB	Descriptive statistics and 95% CI for mean with mBOCF and as observed.	mITT - In patients with a nocturnal stool score ≥1 at baseline	At each scheduled visit.
CCI				At each scheduled visit.
Bristol Stool Scale	Loose stool	Proportion for each weight/treatment dose group along with the 95% 2-sided CI with NRI and as observed	mITT, in patients with loose stool at baseline	At each scheduled visit.

		Analysis Method	Population	
Measure	Variable	(Section 6.1.3)	(Section 6.1.1)	Time Point(s)
EIMs	Resolution of Baseline EIMs	Proportion for each weight/treatment dose group along with the 95% 2-sided CI with NRI and as	mITT – in patients with EIMs at baseline	Weeks 12 and 52
		observed.		

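### Corticosteroid-free remission at Week 52: the SAP ties it to baseline corticosteroid use in Table AMBU.4.2, but drops that condition in Tables AMBU.6.4 and AMBU.6.5

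*SAP*

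**What the plan says.** The SAP describes this secondary endpoint in four places.

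- **Section 4.2, Table AMBU.4.2, objective column:** "corticosteroid-free remission without surgery among patients in clinical remission at Week 52 and receiving" corticosteroids at baseline. Protocol Section 4, Table AMBU.2, has the same objective: "achieving corticosteroid-free remission without surgery among patients in clinical remission at Week 52 and receiving corticosteroids at baseline".
- **Section 4.2, Table AMBU.4.2, endpoint column:** "The proportion of patients who entered the study on corticosteroids and who are in MMS clinical remission at Week 52", without using corticosteroids.
- **Section 6.10.1, Table AMBU.6.4, derivation:** clinical remission at Week 52 plus "No corticosteroid use or UC-related surgery for ≥12 weeks prior to Week 52". Nothing is said about corticosteroids at baseline.
- **Section 6.10.1, Table AMBU.6.5, analysis:** "Corticosteroid-free Proportion for each weight/treatment mITT Week 52". The population is mITT with no qualifier, analysed both with non-responder imputation (NRI) and as observed.

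Two further statements govern how these fit together. The estimand list in Section 4.2 says "The population of interest is described in the protocol inclusion/exclusion criteria and in this document in Section 6.1.1 and Table AMBU.6.4", and sends the reader to Tables 4.2 and 6.4 for the variable. Table AMBU.6.1 defines mITT as all enrolled patients with at least one dose and adds "Unless otherwise noted, efficacy and health outcomes analyses will be conducted on this population".

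**The concern.** The objective is about patients on corticosteroids at entry: do they reach remission and come off them? Reducing corticosteroid use is also one of the three unmet needs in Protocol Section 3.1. A patient with no corticosteroid at baseline has none to withdraw. If such patients enter the count, the reported proportion mixes steroid withdrawal in users with plain remission in non-users. Two programmers working from different SAP tables could report different figures for the same named endpoint, and a reader of the study report could not tell which question had been answered.

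**Working it through.** **Side-by-side reading**

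| Source | Baseline corticosteroids required? | Role of Week 52 remission |
|---|---|---|
| Table 4.2 objective | Yes | Read literally, part of the denominator |
| Table 4.2 endpoint | Yes | Part of the outcome |
| Table 6.4 derivation | No | Part of the outcome |
| Table 6.5 population | No (mITT) | Not applicable |

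The Table 4.2 endpoint wording most naturally makes baseline users the denominator. It can also be read as a joint numerator over mITT. On that second reading the population in Table 6.5 is right, but Table 6.4 still lacks the condition. The mismatch therefore survives either way.

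Section 6.1.1 and Table 6.4, where Section 4.2 places the population, do not contain the restriction. Other rows do write out their subset, such as the Week 12 remitters in Table 6.5 and "mITT, in patients with loose stool at baseline" in Table 6.6. Plain mITT in this row therefore reads as everyone.

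**Size, by illustration only**

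The documents give no rate for this endpoint, so there is no figure to reproduce. Total N of about 30 is from SAP Section 5.2 and the Wilson 95% interval is from SAP Section 6.1.3. Every other count below is an assumption.

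- Baseline users: b = 15, of whom 6 remit and s = 3 of those are free of corticosteroids and surgery for 12 weeks.
- Non-users: 15, of whom 6 remit and k = 6 of those are free of corticosteroids and surgery for 12 weeks.

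Wilson limits, with p = x/n and z = 1.96:

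[p + z²/(2n) ± z·√(p(1−p)/n + z²/(4n²))] / (1 + z²/n)

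For 9/30: (0.300 + 0.064 ± 0.176) / 1.128 = 0.323 ± 0.156, that is 16.7% to 47.9%.

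| Reading | x/n | Proportion | Wilson 95% CI |
|---|---|---|---|
| Tables 6.4 and 6.5 as written, (s + k)/30 | 9/30 | 30% | 16.7–47.9 |
| Table 4.2 endpoint, users as denominator, s/b | 3/15 | 20% | 7.0–45.2 |
| Table 4.2 endpoint, joint numerator over mITT, s/30 | 3/30 | 10% | 3.5–25.6 |
| Table 4.2 objective, literal | 3/6 | 50% | 18.8–81.2 |

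**Sensitivity to k**

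The figure from Tables 6.4 and 6.5 is (3 + k)/30, to be compared with 3/15 = 20%.

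- k = 0: 3/30 = 10%, gap −10 points
- k = 3: 6/30 = 20% (9.5–37.3), gap 0
- k = 6: 9/30 = 30%, gap +10 points

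The gap vanishes only when non-users succeed at the same rate as users, here 3/15 in each.

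**Another assumed split**

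Take 12 users (4 remit, 3 steroid-free) and 18 non-users (6 remit, all steroid-free). The same four readings give 9/30 = 30%, 3/12 = 25% (8.9–53.2), 3/30 = 10% and 3/4 = 75% (30.1–95.4).

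**The case against.** The best defence is that the SAP does state the condition. Table 4.2 is a listed source for the endpoint, and mITT applies only unless otherwise noted, so Table 4.2 could serve as the note. If the endpoint is instead a joint numerator over mITT, Table 6.5 is correct and the defect shrinks to one missing clause in Table 6.4. Both readings are possible. Neither clears Table 6.4, and the SAP names Table 6.4 as a source for both the variable and the population.

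Silence in Table 6.5 is also not proof of a deliberate choice. The weight-change row says only mITT, although Table 4.2 asks for results by gender and age group. That is fair, although gender and age group are stratifiers and do not change who is counted. What sponsor intent lies behind plain mITT is unknown.

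The objective column is not among the SAP's estimand locations, and no analysis table conditions on Week 52 remission. The 3/6 reading is therefore a literal parse of loose wording more than a rival analysis plan. This stands, and the case does not depend on that reading.

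Some definitions cannot be seen. The text after the definition lead-in in SAP Table 4.2, the text after the protocol endpoint and the entry in Protocol Table AMBU.5 are blank or redacted. Nothing is inferred from them; the conflict lies between visible cells. The visible protocol endpoint cell has no baseline restriction and so agrees with Tables 6.4 and 6.5. Even so, the protocol objective beside it carries the restriction.

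Finally, the counts are invented and the consequence is modest. Both points are accepted.

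**Conclusion.** The concern holds. Tables 6.4 and 6.5, followed as written, produce a proportion that includes patients outside the group named in both columns of Table 4.2. This is a conflict between tables and not merely missing detail, and it should be fixed before the analysis is programmed.

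Confidence is high that the tables disagree. It does not extend to which denominator the sponsor intended. Size and direction are unknown, because the numbers of baseline users and of qualifying non-users are not in the documents; the -10 to +10 point range rests wholly on assumed counts.

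The reach is limited. This is one descriptive secondary endpoint in an open-label PK study of about 30 patients, with no treatment comparisons planned (SAP Section 6.2). It is not named in the interim efficacy list (SAP Section 6.16.2), and the PK primary objective is unaffected.

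**What to change.** State the numerator and denominator once and use them throughout.

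- **Table AMBU.6.5:** set the population to mITT patients receiving corticosteroids at baseline, with NRI and as observed.
- **Table AMBU.6.4:** repeat the baseline condition, and say that the denominator is all baseline users, whether or not they are in remission at Week 52. Restricting it to Week 52 remitters would remove the patients whom NRI (SAP Section 6.3.1) counts as failures.
- **Table AMBU.4.2:** align the objective and endpoint columns with this.
- **Protocol objective:** note the difference in the SAP or study report, or align the wording at the next amendment.
- **All-mITT figure:** if wanted, report it labelled as supplementary.

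The work is rewording in three SAP tables. Baseline corticosteroid use is already a Yes/No variable in Table AMBU.6.3.

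The price is precision. In the illustration the Wilson width rises from about 31 points (9/30) to about 38 (3/15). In the >40 kg group of about 10 patients, with an assumed 5 users, it rises from about 50 points (3/10: 10.8–60.3) to about 59 (1/5: 3.6–62.4). Figures by dose group would be descriptive only.
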